## 1. VERSION HISTORY

The statistical analysis plan (SAP) Version 1 for Study B5091009 was based on the protocol dated 01 April 2015. This SAP amendment is based on protocol amendment 1 dated 11 April 2016.

**Table 1. Summary of Major Changes in SAP Amendments**

SAP Version	Change	Rationale
1.0	Not applicable	Not applicable
2.0	Major changes include adding objectives, endpoints, and analysis for the extension stage of the study and an additional interim analysis discussed in protocol amendment 1	Protocol amendment 1, 11 April 2016

## 2. INTRODUCTION

This SAP provides the detailed methodology for summary and statistical analyses of the data collected in Study B5091009. This document may modify the plans outlined in the protocol; however, any major modifications of the primary endpoint definition or its analysis will also be reflected in a protocol amendment.

### 2.1. Study Objectives

#### 2.1.1. Primary Immunogenicity Objectives (PI)

- To describe the immunogenicity of 2 antigen dose levels (100 µg and 200 µg total toxoid) of *Clostridium difficile* vaccine when administered as a 3-dose regimen (Days 1, 8, and 30) to healthy adults aged 65 to 85 years, as measured by *C difficile* toxin A- and toxin B-specific neutralizing antibody levels at Day 37 (7 days after Dose 3).
- To describe the immunogenicity of 2 antigen dose levels (100 µg and 200 µg total toxoid) of *C difficile* vaccine when administered as a 3-dose regimen (Months 0, 1, and 6) to healthy adults aged 65 to 85 years, as measured by *C difficile* toxin A- and toxin B-specific neutralizing antibody levels at Month 7 (1 month after Dose 3).

#### 2.1.2. Primary Safety Objective (PS)

- To assess the safety and tolerability of 2 antigen dose levels (100 µg and 200 µg total toxoid) of *C difficile* vaccine when administered as a 3-dose regimen (either Days 1, 8, and 30 or Months 0, 1, and 6) to healthy adults aged 65 to 85 years, by measuring local reactions and systemic events reported on subjects' electronic diaries (e-diaries), adverse events (AEs), and serious AEs (SAEs).

### 2.1.3. Secondary Immunogenicity Objectives (SI)

- To describe the immunogenicity of 2 antigen dose levels (100 µg and 200 µg total toxoid) of *C difficile* vaccine when administered in a 3-dose regimen (either Days 1, 8, and 30 or Months 0, 1, and 6) to healthy adults aged 65 to 85 years, as measured by *C difficile* toxin A- and toxin B-specific neutralizing antibody levels at multiple time points following vaccination.
- To describe the kinetics of the immune response in healthy adults aged 65 to 85 years for up to 12 months following the administration of 3 doses of *C difficile* vaccine.
- To describe the immunogenicity of a fourth dose of *C difficile* vaccine as measured by *C difficile* toxin A- and toxin B-specific neutralizing antibody levels at multiple time points following vaccination.
- To describe the kinetics of the immune response in healthy adults aged 65 to 85 years for up to 36 months following the administration of a fourth dose of *C difficile* vaccine.

### 2.1.4. Secondary Safety Objective (SS)

- To assess the safety and tolerability of a fourth dose of *C difficile* vaccine by measuring local reactions and systemic events reported on subjects' e-diaries, AEs, and SAEs.

### 2.1.5. CCI [REDACTED] (C)

- CCI [REDACTED]
- [REDACTED]
- [REDACTED]

## 2.2. Study Design

This is a Phase 2, placebo-controlled, randomized, observer-blinded study to assess the safety, tolerability, and immunogenicity of 2 antigen dose levels (100 µg and 200 µg total toxoid) of aluminum hydroxide-containing *C difficile* vaccine administered as a 3-dose regimen: either at Days 1, 8, and 30 or at Months 0, 1, and 6.

Subjects will be assigned to 1 of the 2 dosing regimens (Days 1, 8, and 30 or Months 0, 1, and 6) and then randomly assigned in parallel in a 3:3:1 ratio to receive *C difficile* vaccine (100 µg or 200 µg total toxoid) or placebo (saline).

Subjects in both dosing regimens who received the first 3 doses of *C difficile* vaccine (100 µg or 200 µg) will be enrolled into an extension stage. These subjects will receive a fourth dose of either *C difficile* vaccine at the same antigen dose level (100 µg or 200 µg) as they received previously or placebo, approximately 1 year after their third dose. These subjects will be followed for a further 3 years (visits approximately every 6 months) to assess antibody persistence. Subjects originally randomized to placebo in either dosing regimen will not continue into the extension stage.

Approximately 854 healthy adults aged 65 to 85 years will be enrolled at approximately 15 sites in the United States. Subjects withdrawn from the study after randomization will not be replaced, regardless of the reason for withdrawal.

For each dosing regimen, approximately 366 subjects will receive the *C difficile* vaccine (at either 100 or 200 µg total toxoid dose level) and approximately 61 subjects will receive placebo (saline).

**Table 2. Vaccine Groups and Number of Subjects per Group and per Dose Regimen**

Vaccine Group	Vaccine Formulation Description	Dosing Regimen	Number of Subjects
1 a	Aluminum hydroxide-containing C difficile vaccine (100-µg antigen dose)	Days 1,8,30	183
2 a	Aluminum hydroxide-containing C difficile vaccine (200-µg antigen dose)	Days 1,8,30	183
3	Placebo (saline)	Days 1,8,30	61
4 a	Aluminum hydroxide-containing C difficile vaccine (100-µg antigen dose)	Months 0,1,6	183
5 a	Aluminum hydroxide-containing C difficile vaccine (200-µg antigen dose)	Months 0,1,6	183
6	Placebo (saline)	Months 0,1,6	61
Total			854

a. Subjects in these groups will be asked to enter the extension stage

All eligible subjects who received 3 doses of *C difficile* vaccine (Groups 1, 2, 4, and 5) will be asked to enter the extension stage. Subjects enrolled in the extension stage will be rerandomized to receive a fourth dose of either *C difficile* vaccine at the same antigen dose level (100 µg or 200 µg) as they received previously or placebo.

### **3. ENDPOINTS AND BASELINE VARIABLES: DEFINITIONS AND CONVENTIONS**

#### **3.1. Primary Endpoints**

##### **3.1.1. Primary Immunogenicity Endpoints**

At Day 37 (7 days after Dose 3 for subjects receiving the Day 1, 8, and 30 regimen) and at Month 7 (1 month after Dose 3 for subjects receiving the Month 0, 1, and 6 regimen), the proportions of subjects in each vaccine group with:

- Toxin A-specific neutralizing antibody level (neutralization units/mL)  $\geq$  the specified threshold for toxin A;
- Toxin B-specific neutralizing antibody level (neutralization units/mL)  $\geq$  the specified threshold for toxin B; and
- Both toxin A- and toxin B-specific neutralizing antibody levels (neutralization units/mL)  $\geq$  the specified threshold for toxin A and the specified threshold for toxin B, respectively.

CCI

### **3.1.2. Primary Safety Endpoints**

- Numbers and proportions of subjects reporting local reactions (pain, erythema, and induration) and their severity, as self-reported on e-diaries for up to 14 days following Vaccinations 1, 2, and 3.
- Numbers and proportions of subjects reporting systemic events (fever, vomiting, diarrhea, headache, fatigue, new or worsening muscle pain, and new or worsening joint pain) and their severity, as self-reported on e-diaries for up to 14 days following Vaccinations 1, 2, and 3.
- Numbers and proportions of subjects reporting AEs from the first vaccination up to 28 days after the third vaccination, categorized according to the Medical Dictionary for Regulatory Activities (MedDRA).
- Numbers and proportions of subjects reporting SAEs from the first vaccination until 6 months after the third vaccination, categorized according to MedDRA.

## **3.2. Secondary Endpoints**

### **3.2.1. Secondary Immunogenicity Endpoints**

At Day 37 (7 days after Dose 3 for subjects receiving the Day 1, 8, and 30 regimen) and at Month 7 (1 month after Dose 3 for subjects receiving the Month 0, 1, and 6 regimen):

- Toxin A- and toxin B-specific neutralizing antibody levels, expressed as geometric mean concentrations (GMCs) (neutralization units/mL).
- Geometric mean fold rises (GMFRs) from baseline (before Dose 1) in:
  - Toxin A-specific; and
  - Toxin B-specific neutralizing antibody levels (neutralization units/mL).

- Proportions of subjects in each vaccine group with  $\geq 4$ -fold,  $\geq 8$ -fold,  $\geq 16$ -fold, and  $\geq 32$ -fold rises from baseline in:
  - Toxin A-specific;
  - Toxin B-specific; and
  - Both toxin A- and toxin B-specific neutralizing antibody levels (neutralization units/mL).

For subjects receiving the Day 1, 8, and 30 regimen, on Day 1 (immediately before Dose 1), Day 8 (immediately before Dose 2), Day 15 (7 days after Dose 2), Day 30 (immediately before Dose 3), and Months 2 (1 month after Dose 3), 4 (3 months after Dose 3), 7 (6 months after Dose 3), and 13 (12 months after Dose 3); or for subjects receiving the Month 0, 1, and 6 regimen, on Day 1 (immediately before Dose 1), Day 30 (immediately before Dose 2), Day 37 (7 days after Dose 2), Months 2 (1 month after Dose 2) and 6 (immediately before Dose 3), Day 187 (7 days after Dose 3), and Months 12 (6 months after Dose 3) and 18 (12 months after Dose 3):

- Proportions of subjects in each vaccine group with:
  - Toxin A-specific neutralizing antibody level (neutralization units/mL)  $\geq$  the specified threshold for toxin A;
  - Toxin B-specific neutralizing antibody level (neutralization units/mL)  $\geq$  the specified threshold for toxin B; and
  - Both toxin A- and toxin B-specific neutralizing antibody levels (neutralization units/mL)  $\geq$  the specified threshold for toxin A and the specified threshold for toxin B, respectively (these parameters will also be assessed at baseline).

CCI

- Toxin A- and toxin B-specific neutralizing antibody levels, expressed as GMCs (neutralization units/mL).
- GMFRs from baseline in:
  - Toxin A-specific; and
  - Toxin B-specific neutralizing antibody levels (neutralization units/mL).
- Proportions of subjects in each vaccine group with  $\geq 4$ -fold,  $\geq 8$ -fold,  $\geq 16$ -fold, and  $\geq 32$ -fold rises from baseline in:

- Toxin A-specific;
- Toxin B-specific; and
- Both toxin A- and toxin B-specific neutralizing antibody levels (neutralization units/mL).

Baseline in the above endpoints is the associated last measurement prior to the first vaccination on Day 1.

For subjects enrolled in the extension stage; at the fourth dose (immediately before the fourth dose), at Days 8 and 30 after the fourth dose, and at Months 6, 12, 18, 24, 30, and 36 after the fourth dose:

- Proportions of subjects in each vaccine group with
  - Toxin A-specific neutralizing antibody level (neutralization units/mL)  $\geq$  the specified threshold for toxin A;
  - Toxin B-specific neutralizing antibody level (neutralization units/mL)  $\geq$  the specified threshold for toxin B; and
  - Both toxin A- and toxin B-specific neutralizing antibody levels (neutralization units/mL)  $\geq$  the specified threshold for toxin A and the specified threshold for toxin B, respectively (these parameters will also be assessed at baseline).
- Toxin A- and toxin B-specific neutralizing antibody levels, expressed as GMCs (neutralization units/mL).
- GMFRs from baseline in
  - Toxin A-specific; and
  - Toxin B-specific neutralizing antibody levels (neutralization units/mL).
- Proportions of subjects in each vaccine group with  $\geq 4$ -fold,  $\geq 8$ -fold,  $\geq 16$ -fold, and  $\geq 32$ -fold rises from baseline in
  - Toxin A-specific;
  - Toxin B-specific; and
  - Both toxin A- and toxin B-specific neutralizing antibody levels (neutralization units/mL).

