### 2.2.3. Secondary Immunogenicity Endpoints

At Day 37 (7 days after Dose 3 for subjects receiving the Day 1, 8, and 30 regimen) and at Month 7 (1 month after Dose 3 for subjects receiving the Month 0, 1, and 6 regimen):

- Toxin A- and toxin B-specific neutralizing antibody levels, expressed as geometric mean concentrations (GMCs) (neutralization units/mL).
- GMFRs from baseline (before Dose 1) in
  - Toxin A-specific and
  - Toxin B-specific neutralizing antibody levels (neutralization units/mL).

- Proportions of subjects in each vaccine group with  $\geq 4$ -fold,  $\geq 8$ -fold,  $\geq 16$ -fold, and  $\geq 32$ -fold rises from baseline in
  - Toxin A-specific;
  - Toxin B-specific; and
  - Both toxin A- and toxin B-specific neutralizing antibody levels (neutralization units/mL).

For subjects receiving the Day 1, 8, and 30 regimen, on Day 1 (immediately before Dose 1), Day 8 (immediately before Dose 2), Day 15 (7 days after Dose 2), Day 30 (immediately before Dose 3), and Months 2 (1 month after Dose 3), 4 (3 months after Dose 3), 7 (6 months after Dose 3), and 13 (12 months after Dose 3); and for subjects receiving the Month 0, 1, and 6 regimen, on Day 1 (immediately before Dose 1), Day 30 (immediately before Dose 2), Day 37 (7 days after Dose 2), Months 2 (1 month after Dose 2) and 6 (immediately before Dose 3), Day 187 (7 days after Dose 3), and Months 12 (6 months after Dose 3) and 18 (12 months after Dose 3):

- Proportions of subjects in each vaccine group with
  - Toxin A-specific neutralizing antibody level (neutralization units/mL)  $\geq$  the specified threshold for toxin A;
  - Toxin B-specific neutralizing antibody level (neutralization units/mL)  $\geq$  the specified threshold for toxin B; and
  - Both toxin A- and toxin B-specific neutralizing antibody levels (neutralization units/mL)  $\geq$  the specified threshold for toxin A and the specified threshold for toxin B, respectively (these parameters will also be assessed at baseline).
- Toxin A- and toxin B-specific neutralizing antibody levels, expressed as GMCs (neutralization units/mL).
- GMFRs from baseline in
  - Toxin A-specific; and
  - Toxin B-specific neutralizing antibody levels (neutralization units/mL).
- Proportions of subjects in each vaccine group with  $\geq 4$ -fold,  $\geq 8$ -fold,  $\geq 16$ -fold, and  $\geq 32$ -fold rises from baseline in
  - Toxin A-specific;
  - Toxin B-specific; and

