- Both toxin A– and toxin B–specific neutralizing antibody levels (neutralization units/mL).

For subjects enrolled in the extension stage; at the fourth dose (immediately before the fourth dose), at Days 8 and 30 after the fourth dose, and at Months 6, 12, 18, 24, 30, and 36 after the fourth dose:

- Proportions of subjects in each vaccine group with
  - Toxin A–specific neutralizing antibody level (neutralization units/mL)  $\geq$  the specified threshold for toxin A;
  - Toxin B–specific neutralizing antibody level (neutralization units/mL)  $\geq$  the specified threshold for toxin B; and
  - Both toxin A– and toxin B–specific neutralizing antibody levels (neutralization units/mL)  $\geq$  the specified threshold for toxin A and the specified threshold for toxin B, respectively (these parameters will also be assessed at baseline).
- Toxin A– and toxin B–specific neutralizing antibody levels, expressed as GMCs (neutralization units/mL).
- GMFRs from baseline in
  - Toxin A–specific; and
  - Toxin B–specific neutralizing antibody levels (neutralization units/mL).
- Proportions of subjects in each vaccine group with  $\geq 4$ -fold,  $\geq 8$ -fold,  $\geq 16$ -fold, and  $\geq 32$ -fold rises from baseline in
  - Toxin A–specific;
  - Toxin B–specific; and
  - Both toxin A– and toxin B–specific neutralizing antibody levels (neutralization units/mL).

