### 9.2.3. Analysis of the Secondary and Other Immunogenicity Endpoints

GMCs of the toxin A– and toxin B–specific neutralizing antibody levels at each blood sampling time point will be descriptively summarized for each vaccine group, along with associated 2-sided 95% CIs. The CIs will be constructed by back transformation of the confidence limits computed for the mean of the logarithmically transformed assay data based on Student t distribution.

Point estimates and the associated 2-sided 95% exact CIs will be descriptively summarized for each vaccine group for the following immunogenicity endpoints:

1. Proportions of subjects with toxin A–, toxin B–, and both toxin A– and toxin B–specific neutralizing antibody levels (neutralization units/mL)  $\geq$  the specified threshold(s) at each blood sampling time point except for Day 37 (7 days after Dose 3 for subjects receiving the Day 1, 8, and 30 regimen) and Month 7 (1 month after Dose 3 for subjects receiving the Month 0, 1, and 6 regimen).
2. Proportions of subjects with  $\geq$ 4-fold,  $\geq$ 8-fold,  $\geq$ 16-fold, and  $\geq$ 32-fold rises in either toxin A–, toxin B–, or both toxin A– and toxin B–specific neutralizing antibody levels compared to baseline at each postbaseline blood sampling time point.

The GMFRs in toxin A– and toxin B–specific neutralizing antibody levels from before vaccination to after vaccination will be summarized for each vaccine group by geometric means and associated 95% CIs at all postbaseline blood sampling time points. These CIs are also computed by back transformation of the CIs using the Student t distribution for mean difference of measures on the logarithmically transformed assay results (postvaccination relative to prevaccination).

Empirical reverse cumulative distribution curves (RCDCs) will be presented for each toxin A– and toxin B–specific antibody level.

CCI

.

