### 5.2.2. Analyses for Continuous Data

The *C difficile* toxin A- and toxin B-specific neutralizing antibody levels at each blood sampling time point will be summarized by GMCs and the associated 95% CIs for each vaccine group. The GMC will be calculated as the mean of the assay results after making the logarithm transformation and then back transformation to its original scale. Two-sided 95% CIs will be constructed by back transformation of the CI for the mean of the logarithmically transformed assay results computed based on the Student t distribution.

For each *C difficile* toxin A- and toxin B-specific neutralizing antibody levels, a line plot of the GMC and the associated 95% CI over the sampling time points will be provided by vaccine group, separately for each assigned 3-dose regimen in the original planned stage and for the fourth dose in the extension stage.

The GMFRs in toxin A– and toxin B–specific neutralizing antibody levels from before vaccination to after vaccination will be summarized for each vaccine group by geometric means and associated CIs at all postbaseline blood sampling time points. These CIs are also computed by back transformation of the CIs using the Student t distribution for the mean difference of measures on the logarithmically transformed assay results.

For the originally planned stage, empirical reverse cumulative distribution curves (RCDCs) will be presented graphically for each *C difficile* toxin A– and toxin B–specific neutralizing antibody levels for each vaccine group (including placebo) at Day 37 (Visit 5) and all blood sampling time points after Day 37 for the Day 1, 8, and 30 regimen, and at Month 7 (Visit 7) and all blood sampling time points after Month 7 for the Month 0, 1, and 6 regimen.

For the extension stage, RCDCs will also be presented graphically for each *C difficile* toxin A– and toxin B–specific neutralizing antibody level for each vaccine group at Day 8 after Vaccination 4 (Visit 10) and all blood sampling time points after Visit 10.

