## **Figures:**

The antibody-response line plot of GMCs and the associated 95% CI for each toxin A– and toxin B–specific neutralizing antibody level at the above analysis time points will be presented by vaccine group, separately for each regimen in the originally planned stage and the extension stage.

**Endpoints:** GMFRs from baseline in toxin A– and toxin B–specific neutralizing antibody levels

- Analysis time points:

Original planned stage:

For the Day 1, 8, and 30 regimen: Days 8, 15, 30, and 37, and Months 2, 4, 7 and 13  
For the Month 0, 1, and 6 regimen: Days 30 and 37, Months 2 and 6, Day 187, and Months 7, 12, and 18

Extension stage:

at the fourth dose (immediately before the fourth dose), at Days 8 and 30 after the fourth dose, and at Months 6, 12, 18, 24, 30, and 36 after the fourth dose

- Analysis populations: mITT and evaluable immunogenicity populations
- Analysis methodology: See [Section 5.2.2](#)
- Supporting objective: Secondary immunogenicity objective

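### Extension-stage fold rises appear to run from before Dose 1; the readable text plans no paired rise from the pre-Dose-4 sample, and the extension baseline should be stated

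*SAP*

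**What the plan says.** **Baseline.** At first use, SAP 3.2.1 speaks of "Geometric mean fold rises (GMFRs) from baseline (before Dose 1) in" each toxin's antibody level, and Protocol 2.2.3 likewise of "GMFRs from baseline (before Dose 1) in" each toxin's level. After the original-stage lists the SAP adds: "Baseline in the above endpoints is the associated last measurement prior to the first vaccination on Day 1". The extension-stage list comes next. It uses fold rises from baseline without a definition of its own.

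**Time points.** The extension list in Protocol 2.2.3 opens "For subjects enrolled in the extension stage; at the fourth dose (immediately before the fourth dose), at Days 8 and 30 after the fourth dose". SAP 6.2.1 gives the extension time points for GMFRs, and again for fold-rise proportions, beginning "at the fourth dose (immediately before the fourth dose), at Days 8 and 30 after the fourth dose". The original-stage time points for those same two endpoints start at Day 8 or Day 30. Day 1 is absent there, although it appears in the original-stage lists for GMCs and threshold proportions.

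**Method.** SAP 5.2.2 says that rises in antibody "from before vaccination to after vaccination will be summarized for each vaccine group by geometric means and associated CIs", and limits these summaries to postbaseline samples. Protocol 9.2.3 has similar wording: "neutralizing antibody levels from before vaccination to after vaccination will be summarized for each vaccine group by geometric means and associated 95% CIs". Neither says which vaccination is meant.

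**Objective and design.** SAP 2.1.3 sets out a secondary objective on the immunogenicity of Dose 4, measured by neutralizing antibody levels over several time points, and a separate one on kinetics to 36 months. Protocol 1.2.3 gives persistence and the response to Dose 4 as the purposes of the extension, and rerandomizes entrants 1:1 to vaccine or placebo.

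**The concern.** Everyone who enters the extension has already had three active doses. A fold rise counted from before Dose 1 therefore credits Dose 4 with whatever remains of the earlier response. A subject who does not respond at all to Dose 4 can still be tabulated as a ≥4-fold riser after it. Read within one arm, such a figure describes persistence and does not isolate what Dose 4 added. The sample needed to separate the two is drawn at Visit 9 before vaccination, and its GMC is already planned, yet no readable section uses it as the reference for a rise.

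**Working it through.** **Step 1. Which baseline applies to the extension?** SAP 6.2.1, side by side:

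| Endpoint | Day 1 in original-stage list? | Pre-Dose 4 in extension list? |
|---|---|---|
| GMC | yes | yes |
| Threshold proportion | yes | yes |
| GMFR | no | yes |
| Fold-rise proportion | no | yes |

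The SAP removes the baseline sample from its two fold-rise lists but keeps pre-Dose 4 in both. If pre-Dose 4 were the extension baseline, the GMFR there would be 1 and every fold-rise proportion 0 by construction. SAP 5.2.2 gives GMFRs only at postbaseline samples, so pre-Dose 4 counts as postbaseline. The only baseline defined is before Dose 1. The reading is an inference, but a reasonably firm one.

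**Step 2. What the planned fold rise contains.** For one subject:

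rise (post-Dose 4 / pre-Dose 1) = rise (pre-Dose 4 / pre-Dose 1) × rise (post-Dose 4 / pre-Dose 4)

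The first factor is the residue of Doses 1 to 3. The second is the change after Dose 4.

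**Step 3. What planned outputs can and cannot give.**
- *Point estimate: recoverable.* In the same subjects, the ratio of two GMCs (or of two GMFRs from pre-Dose 1) equals the paired GMFR from pre-Dose 4. A simulated set of 80 subjects gave 2.963 both ways.
- *Confidence interval: not recoverable.* It needs the within-subject correlation between the two visits.
- *Fold-rise proportions: not recoverable.* They need each subject's pair of values. In that simulated set, with arbitrary parameters, 92.5% were ≥4-fold from pre-Dose 1 but 31.25% from pre-Dose 4.

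**Step 4. Illustration of the mixing.** Inputs are the Phase 1 GMFRs in Protocol 1.2.3 (aluminum hydroxide groups, ages 65 to 85, 1 month after Dose 3): 42.73 to 80.66 for toxin A and 136.12 to 484.14 for toxin B. A typical (geometric-mean) subject given placebo at Dose 4 stays at or above cut-off k unless titers have fallen by more than GMFR/k.

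| k | Toxin A | Toxin B |
|---|---|---|
| 4 | 42.73/4 = 10.7 to 80.66/4 = 20.2 | 136.12/4 = 34.0 to 484.14/4 = 121.0 |
| 8 | 5.3 to 10.1 | 17.0 to 60.5 |
| 16 | 2.7 to 5.0 | 8.5 to 30.3 |
| 32 | 1.3 to 2.5 | 4.3 to 15.1 |

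The margin is widest at low cut-offs and for toxin B, and narrow for toxin A at ≥32-fold.

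The documents give no waning. To show a range, assume a fall of w-fold with no Dose 4 response. The share still ≥4-fold is Φ(log10(GMFR/(4w))/SD), with the Phase 1 log10 titer SDs from the footnote to Protocol Table 7 (0.41 to 0.62 for A, 0.78 to 1.40 for B) standing in for the fold-rise SD.

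| Assumed w | Toxin A | Toxin B |
|---|---|---|
| 3 | 81% to 98% | 77% to 98% |
| 10 | 52% to 77% | 65% to 92% |
| 30 | 14% to 39% | 52% to 78% |

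**Step 5. Precision of the added summary.** Protocol 9.1 plans 183 per vaccine group, and 183 × 0.88 = 161.04, which reproduces its 161 evaluable. Split 1:1, that is at most 183/2 = 91.5, or 161/2 = 80.5, per Dose-4 arm within regimen and dose level. These are upper bounds, because entry requires consent and eligibility. At n = 80, an observed 40/80 has a Clopper-Pearson 95% interval of 38.6% to 61.4%.

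**The case against.** The strongest reply is that the plan already meets its own objective. That objective names antibody levels at several time points, not a paired rise. The SAP reports GMCs and threshold proportions before and after Dose 4 with intervals, plus reverse cumulative distribution curves from Day 8 after Dose 4. Both Dose-4 arms share the same three-dose history, so a high residual rise would show in the placebo arm next to the vaccine arm. This stands. A reader might infer that the extension cannot describe the fourth-dose response, and the documents do not support that.

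A reader might also take the pre-Dose-1 baseline as stated for the extension. It is not. The defining sentence covers only the endpoints above it, the before-to-after wording names no dose, and each stage is analyzed separately, so a stage-specific reading is not excluded. The extension time points in SAP 6.2.1 also repeat the GMC list almost unchanged and may simply have been carried over. Nor does the remark "these parameters will also be assessed at baseline" settle it: the same remark is attached to original-stage lists that already include Day 1. Step 1 is the evidence that remains.

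Two further points stand. Nothing in the documents requires a ≥4-fold rise from pre-Dose 4 as a responder definition; the study's own benchmark is the threshold. And the redacted parts (Protocol 2.1.5, 2.2.5 and part of 9.2.3; SAP 3.3, 3.4 and parts of 6.3, including Table 7) may already hold such an analysis.

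**Conclusion.** The concern holds as a modest one. By inference from SAP 6.2.1 and 5.2.2, extension fold rises run from before Dose 1. They are a valid persistence measure but do not isolate the Dose 4 response within an arm. The gap in the readable text is limited to the paired interval for the rise from pre-Dose 4 and the fold-rise proportions from that sample. In addition, the extension baseline is not explicitly defined.

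The size of the mixing cannot be fixed from the documents. The ≥4-fold break-even falls of 10.7 to 20.2 (A) and 34 to 121 (B) need no assumed waning, but they do assume that Phase 1 responses carry over. The GMFRs come from the Months 0, 1 and 6 schedule only and may include the 50-µg group. The SDs pool Day 37 and Month 7 and are not stated to be limited to ages 65 to 85. The shares in Step 4 rest on assumed waning and run from 14% to 98%, so they illustrate direction only.

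Priority is low to moderate: the endpoint is secondary and descriptive, with no hypothesis test.

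**What to change.** Unless a redacted section already does so:

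- In SAP 3.2.1, state the baseline for the extension-stage list. Keep the fold rises from before Dose 1 and label them as the persistence measure.
- In SAP 3.2.1, 5.2.2 and 6.2.1, add descriptive GMFRs from the Visit 9 pre-Dose-4 sample with paired 95% intervals (Student t, as in 5.2.2).
- Add the ≥4-, 8-, 16- and 32-fold proportions from the same sample with Clopper-Pearson intervals (as in 5.2.1).
- Present both by Dose-4 arm within regimen and dose level, at least at Days 8 and 30 after Dose 4.
- Align Protocol 2.2.3 and 9.2.3 at the next amendment.

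The cost is one defining sentence and a few extra descriptive tables. No new samples, assays or interval methods are needed.
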